#### 10- Sample size

The sample size was assessed using the G \* power 3.1.9.4 software (Universities Kiel, Germany). The calculation was based on the study of Ammori et al. [11], which reported a mean hospital stay length of  $4.7 \pm 1.125$  days in the OPD group compared to a respective mean of  $8.9 \pm 5.425$  days in the LPD group. After setting the study power at 80% and  $\alpha$  at 0.05, a minimum of 12 patients in each group were required.

---

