#### 4. Background and Rationale:

Total laparoscopic pancreaticoduodenectomy (TLPD) remains one of the most advanced laparoscopic procedures. Owing to the evolution in laparoscopic technology and instrumentation within the past decade, laparoscopic pancreaticoduodenectomy is beginning to gain wider acceptance.(1)

Gagner and Pomp were the first to describe the laparoscopic Whipple procedure in 1994. The long operative times and technical difficulties coupled with the need to develop advanced laparoscopic skills were valid reasons that supported the initial reluctance to pursue these sophisticated minimally invasive operations. Recently, laparoscopic pancreaticoduodenectomy has started to gain wider acceptance as surgeons become more comfortable with laparoscopic technology. As a result, TLPDs have been reported with an increased frequency from institutions internationally.(2-15)

In recent years, total laparoscopic pancreaticoduodenectomy (TLPD) has been introduced as a feasible alternative to open pancreaticoduodenectomy (OPD) when performed by experienced surgeons in laparoscopic and pancreatic surgery. Its application has been gradually increased, but its safety, reproducibility, and oncological outcomes are still debated due to its technical complexity and prolonged operating time. There are different experiences present in the literature regarding indications, surgical techniques, postoperative outcomes, benefits and limitations of this approach, oncological results, learning curve, and costs. There is no standardized surgical technique for TLPD. Different techniques exist for both the demolitive stage and the reconstructive stage. We summarized the different aspects of the surgical technique based on the various experiences reported by different authors. Compared to OPD, TLPD provides the advantages of laparoscopy, i.e., reduced blood loss, decreased postoperative pain, and shorter length of hospital stay, without increasing the rate of postoperative complications or compromising oncological outcomes. With increased experience, more challenging cases may also be approached with this technique, including those requiring major vascular resections or multi-visceral resections.(16)

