## 5. Objectives:

The study aims to determine the advantages and disadvantages of performing total laparoscopic pancreaticoduodenectomy over the open approach and to compare the outcomes aiming to reduce the magnitude of operative morbidity.

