**9- Study outcomes:**

- **Primary outcome:**

- o Operative time
- o Assessment of early post-operative complications including: pain, respiratory complications (collapse, pleural effusion or pneumonia)
- o Incidence of pancreatic and biliary leakage

- **Secondary outcome:**

- o ICU stay and total hospital stay
- o Patient satisfaction in terms of pain, ambulation, ability to resume daily routine activities
- o Blood loss and need for blood transfusion accordingly

- Wound complications including: infection (early) and incisional hernia/port site hernia (late)
- Pathological assessment in terms of LN harvesting and resection margins (R0 resection or R1)

---

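### The stated 80% power and 12 patients per group rest on hospital stay alone, a secondary outcome; no planning value or power is given for any primary outcome

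*Combined protocol and SAP*

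**What the plan says.** Section 10 (Sample size) uses one outcome. It cites a study "which reported a mean hospital stay length of" 4.7 ± 1.125 days in the open group and 8.9 ± 5.425 days in the laparoscopic group. The next sentence opens "After setting the study power at 80" per cent, with alpha 0.05, and concludes that "a minimum of 12 patients in each group were required". The software is named. The test, its sidedness and the SD entered are not.

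Section 9 (Study outcomes) lists "ICU stay and total hospital stay" under the secondary outcomes. Its primary list has three items: operative time; early complications, comprising pain and respiratory complications; and "Incidence of pancreatic and biliary leakage".

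No section gives an expected mean, SD, rate, difference or power for any primary outcome. Section 11 (Statistical analysis) has a heading and no text. The only complication figure, 24–59% in Section 4, is a background range for overall morbidity after the operation. It is not split by approach and is not used for sizing.

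**The concern.** Section 10 speaks of the power of the study, without limiting it to hospital stay. A reader who goes from Section 9 to Section 10 may take the 80% as the chance of detecting a relevant difference in the primary outcomes. Nothing in the plan supports that.

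The main consequence is for leakage and respiratory complications. Section 5 describes the trial as "aiming to reduce the magnitude of operative morbidity", and Section 4 already reports that laparoscopy brings its benefits "without increasing the rate of postoperative complications". With 12 per group, a non-significant comparison of complications is compatible with a large true difference. If readers believe that the trial had 80% power for these outcomes, they may take such a result as support for the Section 4 statement.

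**Working it through.** **1. Reproducing the plan's figure (hospital stay).** Inputs from Section 10: means 4.7 and 8.9 days, ± figures 1.125 and 5.425 (taken as SDs), alpha 0.05, power 80%, equal groups.

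- Difference: 8.9 − 4.7 = 4.2 days.
- Root-mean-square SD: √((1.125² + 5.425²)/2) = √15.348 = 3.918.
- Standardised difference: d = 4.2/3.918 = 1.072.
- Power from the noncentral t distribution with 2n − 2 degrees of freedom and noncentrality d√(n/2). At n = 12 the noncentrality is 1.072 × √6 = 2.626.

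| t-test, SD 3.918 | Power at 12 per group | Smallest n per group for 80% |
|---|---|---|
| One-sided 0.05 | 81.6% | 12 (11 gives 78.3%) |
| Two-sided 0.05 | 70.9% | 15 (14 gives 77.9%; 15 gives 80.9%) |

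So the plan's 12 is reproduced exactly by a one-sided t-test with this SD. The SD choice also matters. With the simple average SD, (1.125 + 5.425)/2 = 3.275, two-sided power at 12 per group is 85%. With the larger SD, 5.425, it is 44%. Section 10 does not say which was used.

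**2. Looking for the same inputs for the primary outcomes.**

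| Primary outcome (Section 9) | Planning value in the plan | Power in the plan |
|---|---|---|
| Operative time | none | none |
| Pain | none | none |
| Respiratory complications | none | none |
| Pancreatic and biliary leakage | none | none |

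No power can therefore be computed for them from the plan. What can be computed is the true difference that 12 per group would detect.

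**3. What 12 per group can detect.** Assumptions: 80% power, two-sided 0.05 for each outcome separately, no multiplicity adjustment, no dropout. The tests are assumed because none is named.

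*Continuous outcomes (t-test, 22 degrees of freedom).* Solving the noncentral t for 80% gives d = 1.197, about 1.2 SD. At 0.8 SD the power is 47%, and at 0.5 SD it is 22%.

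*Binary outcomes.* Power is the sum, over all pairs of event counts from 0 to 12, of the binomial probabilities of those pairs that the test rejects. All rates are assumed.

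| Assumed lower rate | Higher rate for 80% power, Fisher | Higher rate for 80% power, uncorrected chi-square |
|---|---|---|
| 0% | about 50% | about 41% |
| 10% | about 68% | about 61% |

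As an illustration, take the two ends of the Section 4 range as if they were the two arms, 59% vs 24%. Power at 12 per group is 29% by Fisher and 46% by uncorrected chi-square.

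*Precision.* With no events among 12 patients, the exact 95% upper limit is 1 − 0.025^(1/12) = 0.2646, about 26%.

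**The case against.** **The power statement directly follows the sentence on hospital stay, so a careful reader sees what is powered.** This is fair as to how Section 10 reads on its own. It does not answer the mismatch with Section 9, and the text never says that the primary outcomes are unpowered.

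**The binary figures depend on the test and on invented rates.** This stands. The gap needed at a lower rate of 0% is about 50 percentage points by Fisher but about 41 by uncorrected chi-square, so neither is a property of 12 per group alone. The 59% and 24% are ends of an overall complication range, not leakage or respiratory rates by arm. Such figures belong in the protocol only beside a named test and labelled as assumed.

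**Low power is not shown for operative time or pain.** This also stands. A reader might infer that the trial is underpowered for every primary outcome. The documents do not support that: without an SD or an expected difference, nobody can say whether 1.2 SD is large for operative time. What is established is that adequate power has not been shown.

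**No equal-safety conclusion is planned.** Correct. A reader might infer from Section 4 that the trial sets out to confirm equal complication rates. That sentence is background on published experience, and no section plans such a claim. The risk lies in how a null result might be read.

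**A wording change is a weak remedy; the trial should name one primary outcome and size for it.** That would be the stronger repair. It needs a planning value that the documents do not contain, and probably more patients. Correcting what the 80% refers to is needed in either case.

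**Conclusion.** The point holds and should be corrected. The stated 80% is tied to hospital stay, a secondary outcome, and has no demonstrated bearing on operative time, pain, respiratory complications or leakage. This rests on reading Sections 9, 10 and 11 together and on no assumption about tests or rates.

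For hospital stay itself, a reader might infer that the calculation is wrong. That goes too far: 12 is exactly right for a one-sided t-test with SD 3.918, and the average SD gives more than 80% two-sided. The supported statement is conditional. If the test is two-sided with SD 3.918, power at 12 per group is about 71%, and 15 per group would be needed. This takes the ± figures as SDs and assumes approximately normal data.

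The detectable differences carry the assumptions listed with them. On either binary test shown, only very large differences in leakage or respiratory complications would be detected with 80% power.

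**What to change.** **Section 10.**
- State that the 80% concerns hospital stay only and is not the power for the primary outcomes.
- State the test, sidedness and SD entered in the software. If the test was two-sided with SD 3.918, restate the power at 12 per group as about 71%.
- Add what 12 per group detects with 80% power at two-sided 0.05 per outcome, unadjusted for multiplicity: about 1.2 SD for operative time and pain by t-test. For leakage and respiratory complications, name the test and give the matching figures, labelled as assumed rates: about 0% vs 50% or 10% vs 68% by Fisher, or about 0% vs 41% or 10% vs 61% by uncorrected chi-square.

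**Section 11.** Report leakage and respiratory complications as estimates with exact 95% confidence intervals. State that a non-significant difference will not be read as equal safety.

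**If hospital stay is made primary instead.** Restate its power as above. Also reconcile Section 10, where the laparoscopic group stays longer (8.9 vs 4.7 days), with Section 4, which credits laparoscopy with a "shorter length of hospital stay". With a two-sided t-test and SD 3.918, 15 per group means 30 patients, 6 more than the present minimum of 24.

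**Cost.** With the present primary outcomes kept, this is wording only, with no extra patients. The stated power will look less favourable, and disclosure does not raise the power for any primary outcome. Raising it needs a named primary outcome with a planning value. As a guide, 80% power at two-sided 0.05 takes 26 per group for 0.8 SD, 64 per group for 0.5 SD, or about 36 per group for an assumed 59% vs 24% by Fisher.

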#### 11- Statistical analysis

#### 12- Source of funding:

- No Funding

---

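### The 12 per group in Section 10 reproduces only as an undeclared one-sided t-test (equal-weight SD); two-sided power on the printed figures is about 71% (pooled t) or 67% (Welch), not 80%

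*Combined protocol and SAP*

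**What the plan says.** Section 10 (Sample size) names G*Power 3.1.9.4 as the software and takes its inputs from one cited study of hospital stay: 4.7 ± 1.125 days for open surgery (OPD) and 8.9 ± 5.425 days for laparoscopic surgery (LPD). The targets are 80% power and alpha 0.05, and the result is "a minimum of 12 patients in each group were required". The section does not say whether the test is one- or two-sided, which test was chosen, or which SD or effect size was entered.

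No other section fills the gap. "11- Statistical analysis" is a heading with no text beneath it. Section 9 lists "ICU stay and total hospital stay" among the secondary outcomes. Section 5 (Objectives) sets out to find both the advantages and the disadvantages of the laparoscopic approach.

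The direction of the expected effect is not consistent. Section 4 credits laparoscopy with "reduced blood loss, decreased postoperative pain, and shorter length of hospital stay", while Section 10 attaches the longer mean stay to the LPD group.

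**The concern.** This is the document's only justification for its sample size, and a reader cannot reproduce it without guessing a setting. The setting that reproduces it most directly is a one-sided test. That would have to be declared in advance with a direction. The plan declares neither, its objective looks in both directions, and Sections 4 and 10 point opposite ways on hospital stay.

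If the analysis is two-sided, the stated 80% is not what 12 per group delivers under the normal model behind a t-test calculation. The chance of missing the planned 4.2-day difference would be about 29% to 33% rather than 20%.

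**Working it through.** **Inputs.** From Section 10: means 4.7 and 8.9 days, SDs 1.125 and 5.425 days, alpha 0.05, power 80%, equal groups of 12. Assumed, because not stated: a two-sample t-test and equal-weight pooling of the two SDs.

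**Effect size.**
- Difference: 8.9 − 4.7 = 4.2 days.
- Pooled SD: √[(1.125² + 5.425²)/2] = √[(1.2656 + 29.4306)/2] = √15.348 = 3.918.
- d = 4.2/3.918 = 1.072.

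**Power.** The t statistic has 2n − 2 degrees of freedom and noncentrality d√(n/2). At n = 12 this is 1.072 × √6 = 2.626 on 22 df, with critical values 1.717 (one-sided) and 2.074 (two-sided).

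| n per group | one-sided 0.05 | two-sided 0.05 |
|---|---|---|
| 11 | 78.3% | 66.7% |
| 12 | **81.6%** | **70.9%** |
| 14 | 86.8% | 77.9% |
| 15 | 88.9% | 80.9% |

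The plan's figure is therefore reproduced exactly by a one-sided t-test. Under the same pooling, other candidates do not give 12:
- normal approximation: 11 one-sided, 14 two-sided;
- Wilcoxon–Mann–Whitney with the normal efficiency factor: 13 and 16;
- Wilcoxon–Mann–Whitney with other parent distributions: 8 to 14 one-sided and 10 to 17 two-sided, none equal to 12.

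**Unequal SDs.** The two SDs differ almost five-fold, so Welch's test is a natural alternative. With normal data, two-sided Welch power is about 67% at 12, 78% at 15 and 81% at 16, so 80% needs 16 per group. Simulated two-sided power of the pooled t-test with the two separate SDs at n = 12 is about 71%, matching the formula.

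**Detectable difference.** At n = 12, two-sided 80% power needs d = 1.197, that is 1.197 × 3.918 = 4.69 days rather than 4.2.

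**Sensitivity to the SD entered.** The cited study's group sizes are not given, so a size-weighted pooled SD cannot be ruled out. Let w be the weight on the larger variance, so SD² = w × 5.425² + (1 − w) × 1.125². A required n of 12 needs:
- two-sided: SD 3.34 to 3.51 (w about 35% to 39%);
- one-sided: SD 3.83 to 4.01 (w about 47% to 53%).

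| w (assumed range) | 30% | 40% | 50% | 60% | 70% |
|---|---|---|---|---|---|
| two-sided power at n = 12 | 88% | 79% | 71% | 64% | 57% |

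Entering the simple average of the SDs, 3.275, gives 85% at 12 and a two-sided minimum of 11.

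**Sensitivity to shape.** Same means and SDs, n = 12, two-sided, simulated:

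| Assumed distribution | Welch | pooled t |
|---|---|---|
| normal | 67% | 71% |
| gamma | 74% | 78% |
| lognormal | 80% | 83% |

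**The case against.** **The arithmetic is not shown to be wrong.** The printed 12 follows exactly from a standard one-sided test. What is certain is a reporting gap; the power shortfall follows only if the intended test is two-sided. That is correct. But a one-sided 12 needs a declaration and a direction, and the plan gives neither.

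**Another SD may have been entered.** A two-sided 12 follows from an SD of 3.34 to 3.51, and this cannot be excluded. It affects how 12 was obtained more than what 12 delivers. With 12 against 12 and the printed SDs, the standard error of the difference is √[(1.125² + 5.425²)/12] = 1.60 days, whatever SD was typed in. If those SDs hold in this trial and the data are normal, two-sided power remains about 71% or 67%.

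**Normality is doubtful.** A normal distribution with mean 8.9 and SD 5.425 puts about 5% of stays below zero days (−8.9/5.425 = −1.64). Under the skewed alternatives above, the chance of a miss falls to about 17% to 27%. This stands as a limit on the headline figures. Skew does not help every test, however: a rank test at n = 12 gave about 62% to 73% in simulation. The plan names neither a distribution nor a test.

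**The consequence is limited.** Hospital stay is a secondary outcome, and sizing the trial on it while Section 11 is empty is the larger weakness. That is fair, and it is why the remedy here is one of statement rather than redesign. Likewise, the conflict over direction sets a general literature summary against a single study. It calls for a check of the labels and is not proof of an error.

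**Conclusion.** The concern holds. The omission of tails, test and SD is certain. On the printed means and SDs with equal-weight pooling, 12 per group is the minimum only for a one-sided t-test that the document does not declare. At two-sided 0.05 with normal data, power is 70.9% (pooled t) or about 67% (Welch), 9 to 13 percentage points below the stated 80%; restoring 80% would take 15 or 16 per group.

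These figures rest on the printed SDs applying in both arms of this trial and on stays being close to normal. Confidence is medium because the SD actually entered is unknown and skew could bring t-test power back to around 80%. Nothing here bears on power for the primary outcomes.

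**What to change.** Keep 12 per group. In Section 10, state that the test is two-sided at 0.05, state the SD used, and replace the closing sentence with wording such as:

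> *With 12 patients per group and the means and SDs above, two-sided power at alpha 0.05 for hospital stay (a secondary outcome) is about 71% with a pooled t-test (about 67% with Welch's test), assuming normal data.*

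If a different SD was entered in G*Power, give that SD instead and show that it reproduces 12 two-sided. If a one-sided test was in fact intended, that must be declared, with its direction and justification. Before restating, check the OPD and LPD labels on the two means against Section 4; swapping them leaves the two-sided figures unchanged.

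The cost is one restated sentence and a check of two labels, with no change to design or recruitment. The drawback is a less favourable stated power, about 67% to 71% instead of 80%, unless another SD entry accounts for the 12.

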#### 11- Statistical analysis

#### 12- Source of funding:

- No Funding

---

#### 13- Time plan:

- When to start? After REC approval
- When expected to finish?
- When to publish?

---

